Criteria	Klinefelter syndrome or Y-chromosome microdeletions), hypogonadotropic hypogonadism (that might respond to gonadotropin injections), the use of anabolic steroids, illicit drugs, or the consumption of more than 4 alcoholic beverages daily, severe mental health problems, or current therapy with retinoic acid (e.g. Accutane) or vitamin A.

Efficacy	In this study, count of total, motile sperm after 24 weeks of
Parameters	treatment.
Safety	CBC, clinical chemistry panel (glucose, liver and renal
Parameters	function tests including urea, creatinine, albumin, alanine aminotransferase, aspartate aminotransferase, alkaline phosphatase, bilirubin), full lipid panel including Total cholesterol, HDL, LDL, triglycerides at screening and at the end of treatment. Additional measures will be conducted if any abnormal values are found until the end of study visit. • Adverse event and concomitant medications throughout the study. Other safety parameters include vital signs; and changes in pre- and post-treatment physical examination results and score on the PHQ9 depression questionnaire.
Evaluations	The following determinations will be made in all subjects: • Serum samples will be collected for the measurement of concentrations of vitamin A, all-trans and 13-cis retinoic acid, testosterone, FSH and LH will be collected before the beginning of the treatment, and monthly during treatment.
Other Assessments	Demographic characteristics, including age and race, will be collected
Statistical	The primary endpoint is the effect of treatment on the count
	of total, motile sperm between treatment groups after 24
Analysis	weeks. This analysis will be conducted using a Kruskal-Wallis ANOVA is the primary endpoint.

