This data suggests that lower intratesticular retinoic acid is associated with impaired spermatogenesis; however, it is unclear from this cross-sectional data if the low retinoic acid is a result of the infertility or a cause of it. Only an interventional trial of retinoic acid in infertile men will answer the question of the ability of retinoic acid to improve spermatogenesis in this population.

Objectives

2.1 Primary Objective:

To determine the effect of 13-cis retinoic acid administration on total motile sperm count in men with oligoasthenoteratozoospermia

2.2 Secondary Objectives:

- o To determine the chance of pregnancy during treatment with 13-cis retinoic acid
- o To determine the concentration of 13-cis retinoic acid in the seminal plasma of treated men
- o To determine the side effects and tolerability of treatment with 13-cis retinoic acid

3. Rationale, Benefits and Risks

Male infertility is common and difficult to treat unless men have an easily identified gonadotropin deficiency. Many men have idiopathic infertility. Retinoids are necessary for spermatogenesis, but no controlled studies of retinoic acid administration to men with infertility have been conducted. We have shown that men with abnormal spermatogenesis have lower than normal levels of intratesticular retinoic acid, suggesting that intratesticular retinoic acid deficiency is associated with infertility. In this study, we aim to determine if retinoic acid therapy can improve sperm counts in men with low sperm counts. The medication, 13-cis retinoic acid is widely available and prescribed for the treatment of acne, suggesting that serious adverse events, especially at the low doses to be tested are unlikely.

4. Compliance

All aspects of this study will be performed according to GCP and ICH guidelines, under an active IND.

5. Study Design

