We will conduct a prospective, three-arm, randomized, double-blinded, placebo-controlled interventional trial to determine the impact of therapy with 13-cis retinoic acid on sperm indices in infertile men. Sixty (n=20/group) infertile men with abnormal sperm analyses will be enrolled in a 24-week study of 20mg or 40 mg of 13-cis retinoic acid or matching placebo daily. The subjects will be closely followed for side effects related to treatment. The impact of treatment on indices of spermatogenesis will be determined by monthly seminal fluid analyses. All aspects of this study will be performed in compliance with Good Clinical Practice (GCP) regulations, ICH guidelines, the Declaration of Helsinki, and under an FDA Investigational New Drug (IND) application.

6. Duration of the Study

Subjects: Subjects will undergo a screening phase of up to 60 days. After fulfilling all entry criteria, the first 60 subjects will be randomly assigned to one of the three groups. The treatment phase will last for 24 weeks and subjects will have two post-treatment visits, about 4 and 12 weeks after the end of treatment.

Enrolment should be completed in approximately 12 months, resulting in total study duration of about 24 months including screening, treatment phase, end of study visit procedures, close out and data analysis.

7. Number of Subjects

60 men will participate in the study (n=20/arm)

8. Dosage and Administration

13-cis retinoic acid at 20 or 40 mg daily (purchased commercially) or matching placebo

9. Selection of Subjects

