12.2 Laboratory Samples

Blood samples for laboratory analyses will be collected at the two screening visits, Day 1 and at the treatment visits every four weeks with the subject in a fasting state (no food or drink other than 4 to 6 ounces of water or non-sweetened clear liquids for a minimum of 10 hours). If the subject is in a non-fasting state, the investigator will reschedule the visit within two days. The investigator will review all laboratory reports and file a copy with each subject's chart and CRFs. The CBC and blood chemistry samples will be analysed at the local hospital laboratory at the University of Washington.

The serum samples for measurements of retinoic acid will be frozen for analysis at the end of study to prevent inadvertent breaking of the blind. Briefly, the blood samples will be collected into vacutainers (containing serum separating tube gel and clot activator) and gently mixed. After wrapping in aluminum foil to prevent light exposure that can degrade retinoic acid, samples will be allowed to clot for 1-2 hours at room temperature before centrifugation at 1000-2000g for 15 minutes. Following centrifugation, the serum samples will be frozen at -20 C.

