12.3.1 Screening Visit

The following screening procedures will be performed at the screening visit:

• Each participant must sign an IRB-approved informed consent form before any of the study-related procedures can be performed. The original signed informed consent form will be kept on file by the investigator with the subject's record and a signed copy will be given to the subject.

- A screening number will be assigned.
- A general medical history will be taken and will include information on current and previous diseases and treatment.
- Vital signs (pulse, blood pressure and respiratory rate) will be taken and recorded.
- Complete physical exam including measurement of testicular volume will be performed.
- Fasting blood samples will be obtained for the following measurements: Complete blood count (CBC), clinical chemistry including glucose, liver and renal function tests (urea, creatinine, albumin, alanine aminotransferase, aspartate aminotransferase, gamma glutamine transferase, alkaline phosphatase, bilirubin, albumin, full lipid panel including total cholesterol, HDL, and LDL, triglycerides, hematology (hematocrit, hemoglobin), and hormones (LH, FSH, T)
- Semen analysis will be done to measure sperm concentration, motility and morphology
- Height and weight will be collected
- Participants will be questioned regarding concomitant medications and adverse events.
- Once lab results are obtained and considered consistent with idiopathic infertility by the investigator as per the inclusion/exclusion criteria for enrollment, the participant is informed by telephone of his lab results. If conformance to the inclusion/exclusion is confirmed, he is scheduled to return to the clinic for the 2nd sperm collection. If this 2nd sperm collection also meets enrollment criteria, the subject is schedule to begin on treatment
- Successful volunteers will be assigned subject numbers in sequence as they meet the study requirements.
- If any results are abnormal, according to local laboratory standards and in the clinical judgment of the investigator, the subject will be informed and excluded from the study and referred to his primary physician.

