12.4.1 Visit 1 (week 0)

This is the day 1 of treatment. The following will be done at this visit:

- Vital signs (pulse, blood pressure, respiratory rate) and weight will be taken and recorded.
- Subjects will be questioned regarding concomitant medications and adverse events. If the subject is taking a medication that is listed as disallowed the subject should not be enrolled in the study.
- The subject will complete the PHQ9 questionnaire (see appendix xx)
- A blood samples will be drawn, and the time of day of the blood draw will be noted in the CRF.
- A semen sample will be obtained for the measurement of sperm count, concentration, motility and morphology.
- Subjects will be given enough supply of study medication for 30 days (plus a supply for 2 additional days in the event of scheduling issues) as per their assigned group.
- A study medication log will be dispensed to record the date and time of administration of the study medication. Subjects will be instructed to take the medication in the morning, except on the day of the visit. Subjects will be scheduled to return to the clinic after 28 ± 4 days.

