12.4.2 Visits 2-7

These visits are for weeks 4,8,16, 20 and 24. The following procedures will be done at each of these visits:

- Vital signs (pulse, blood pressure, respiratory rate) and weight will be taken and recorded.
- The subject will complete the PHQ9 questionnaire
- Complete physical exam including testicular examination and volume measurement will be performed.
- Subjects will be questioned regarding concomitant medications and adverse events.
- Any unused study medication will be collected at this visit.
- Study medication log will be reviewed to check the date and time of drug administration. These logs will be collected at this visit.

 A blood sample will be drawn. The time of day of the blood draws will be recorded in the source.

- A semen sample will be obtained for the measurement of sperm count, concentration, motility and morphology
- Fasting blood samples will be obtained for the following measurements: CBC, clinical chemistry including glucose, liver and renal function tests (urea, creatinine, albumin, alanine aminotransferase, aspartate aminotransferase, gamma glutamine transferase, alkaline phosphatase, bilirubin, and albumin), full lipid panel including total cholesterol, HDL and LDL, triglycerides, hematology (hematocrit, hemoglobin), and testosterone, FSH and LH. In addition, two serum samples will be frozen for the future analysis of serum retinoid levels.
- Subjects will be given the next month's supply of medication.
- Subjects will be scheduled to return to the clinic after additional 4 weeks visit.

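### Seminal-plasma 13-cis retinoic acid is a secondary objective, but the plan specifies no handling, assay, endpoint or summary for it

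*Combined protocol and SAP*

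**What the plan says.** The synopsis and section 2.2 give three secondary objectives: pregnancy, side effects, and "To determine the concentration of 13-cis retinoic acid in the seminal plasma of treated men". These are the only two places where seminal plasma is mentioned.

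For retinoids, the synopsis (Evaluations) states "Serum samples will be collected for the measurement of concentrations of vitamin A, all-trans and 13-cis retinoic acid". Section 12.2 adds "The serum samples for measurements of retinoic acid will be frozen for analysis at the end of study to prevent inadvertent breaking of the blind" and describes light protection, clotting, centrifugation and freezing, all for blood tubes. Section 12.4.2 says that "two serum samples will be frozen for the future analysis of serum retinoid levels". Section 12.4.3 draws blood for retinoids at follow-up, and Appendix 1 puts retinoids among its blood-sampling rows.

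For semen, section 5 says "The impact of treatment on indices of spermatogenesis will be determined by monthly seminal fluid analyses". The screening text in section 12.3.1 says "Semen analysis will be done to measure sperm concentration, motility and morphology". From Day 1 onward the visit text says "A semen sample will be obtained for the measurement of sperm count, concentration, motility and morphology", and the same purpose is given for visits 2-7 and for follow-up.

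The secondary endpoints in section 14 cover sperm quality, pregnancies and side effects. It also plans a linear regression relating baseline or change in retinoid concentration to change in sperm quality, without saying in which fluid the concentration is measured. Section 14.2 describes total motile sperm count only.

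**The concern.** An objective needs a sample, a measurement and a reported quantity. Here the objective is worded for seminal plasma, while the procedures lead only to serum. A serum concentration is not an answer to a question about seminal plasma. Within this trial semen is the only reproductive-tract sample, and the rationale in sections 1 and 3 concerns retinoic acid in the testis.

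Timing matters. Retinoid assays are deferred to the end of the study to protect the blind, so a site following the visit text could finish collection before anyone noticed that no seminal plasma had been set aside. The protocol also recognises that handling matters for this analyte: blood is processed "After wrapping in aluminum foil to prevent light exposure that can degrade retinoic acid". That step is written for blood. Extending it to semen is an inference, though a reasonable one.

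**Working it through.** No calculation applies: the point depends on no alpha, power, effect size or variance, and the plan gives no figure to reproduce. The check is to follow each secondary objective through to its measurement and its analysis.

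| Secondary objective | Measurement specified | Listed in section 14 |
|---|---|---|
| Pregnancy during treatment | Not examined for this point | Yes |
| Side effects | Adverse events, laboratory tests, PHQ-9 | Yes (also 14.3) |
| Seminal-plasma 13-cis retinoic acid | None for seminal plasma | No |

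**Step 1, the retinoid side.** The synopsis Evaluations and sections 12.2, 12.4.2 and 12.4.3 name serum or blood, and Appendix 1 lists retinoids under blood sampling. None names semen or seminal plasma. The serum instructions in 12.2 are complete in themselves and do not extend to another fluid.

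**Step 2, the semen side.** Sections 12.3.1, 12.4.1, 12.4.2 and 12.4.3 give sperm indices as the only purpose of the sample. Appendix 1 has one semen row, for semen analysis. None mentions a retinoid measurement or retention of the fluid part.

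**Step 3, the analysis side.** The section 14 endpoints cover 2 of the 3 secondary objectives, leaving 3 - 2 = 1. The regression is the only retinoid analysis. Its matrix is unstated, and the written procedures would supply serum values alone. Even if seminal plasma were meant, a regression on change in sperm quality does not report the concentration in treated men, which is what the objective asks for.

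**Step 4, what could be used.** Appendix 1 schedules semen at Day 1, at six on-treatment visits (weeks 4, 8, 12, 16, 20 and 24) and at two follow-up visits. The active arms have 2 × 20 = 40 men, so up to 40 × 6 = 240 on-treatment semen samples from treated men are planned before drop-out. At week 24 alone the figure is 40, or 40 × 0.9 = 36 if the 10% drop-out allowed for in section 14.1 applied evenly. The specimens exist in the plan; the instruction to keep and assay their plasma does not.

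**The case against.** Four points on the other side deserve weight.

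- **Semen is already scheduled.** A reader might infer that the trial has no specimen for this objective. The documents do not support that: the source specimen is collected throughout. What is missing is handling, assay and summary.
- **Loss is not certain.** A reader might infer that the data are bound to be lost. The documents do not say what happens to semen left after analysis, and the consent pages were not available. The loss follows only if the plasma is not kept.
- **The endpoint list is open-ended, and a regression is planned.** Section 14 introduces its secondary endpoints with wording that need not be exhaustive, so absence from the list is weaker evidence than absence from a closed one. It would also be wrong to say that retinoids have no analysis at all. But no other section supplies the endpoint, and the regression does not report the concentration.
- **Repetition is not size.** Several sections omit seminal plasma, but they repeat near-identical visit text. Counting them shows one omission many times over, not a larger one.

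The abbreviation list includes LC/MS, which hints at an assay, but no procedure uses the term or ties it to a fluid. The core gap stands after all of these.

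**Conclusion.** The concern holds in this form: the plan states a seminal-plasma objective, specifies nothing that would turn the semen it collects into a seminal-plasma measurement, and lists no endpoint or descriptive summary for it. Followed as written, it cannot answer 1 of its 3 secondary objectives.

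This rests on two assumptions: that sites do what the visit text says and no more, and that no laboratory manual outside these documents covers seminal plasma. If plasma is in fact being kept under suitable conditions, the remaining gap is one of documentation and analysis.

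A reader might infer that the trial's main conclusion is weakened. It is not: the objective is descriptive and secondary, and the primary endpoint and sample size do not depend on it. The point is a cheap improvement, best made before semen collection starts.

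**What to change.** Choose one option and make all sections agree.

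**(A) If the measurement is intended.** In the synopsis Evaluations, section 12.2, the visit text and Appendix 1, state that seminal plasma left over from semen already collected at one or more named on-treatment visits is separated, protected from light, frozen, and assayed for 13-cis retinoic acid at the end of the study to protect the blind. Week 24 should be included, and ideally Day 1 as well; one on-treatment visit would meet the objective as worded. Name the assay. In section 14, list the concentration as a secondary endpoint with n, median and interquartile range by arm, and name the matrix used in the regression.

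Cost: aliquoting, light protection, freezer space and assay runs. Week 24 in all arms is at most 60 samples; adding Day 1 makes it at most 60 + 60 = 120. Assay performance in seminal plasma, the volume remaining after semen analysis, and consent coverage for stored semen need checking. No new patient procedure is required.

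**(B) If it is not intended.** Delete the objective from the synopsis and section 2.2, or restate it there as serum 13-cis retinoic acid. If it is restated, list the serum concentration in section 14 as a secondary endpoint with the same descriptive summary. In either case, name serum as the regression matrix.

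Cost: text changes only, but the seminal-plasma question is given up.

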9.1.1 Inclusion Criteria

1. Subjects will be infertile men (no pregnancy with partner with normal cycles and normal hysterosalpingogram despite >1 year of unprotected intercourse).

- 2. Abnormal sperm analyses with a total, motile sperm count of less than 10 million sperm as assessed by semen analysis on two occasions separated by one week.
- 3. In the opinion of the investigator, is able to comply with the protocol, understand and sign an informed consent and HIPAA form.

9.2 Exclusion Criteria

Men who meet any of the following criteria are NOT eligible for enrollment in the trial:

- 1. Men participating in another clinical trial
- 2. Men not living in the catchment area of the clinic
- 3. Clinically significant abnormal findings at screening
- 4. Known genetic infertility (e.g. Klinefelter syndrome or Y-chromosome microdeletions),
- 5. Hypogonadotropic hypogonadism (that might respond to gonadotropin injections),
- 6. The use of anabolic steroids, illicit drugs, or the consumption of more than 4 alcoholic beverages daily
- 7. Severe mental health problems requiring medications
- 8. Current therapy with retinoic acid (e.g. Accutane) or vitamin A.
 - 9. Abnormal serum chemistry values according to local laboratory normal values, which indicate liver or kidney dysfunction. Other abnormal lab values may also be exclusionary, at the discretion of the investigator

10. Concomitant Treatment

Concomitant medications that are exclusionary include:

- Use of sex hormones for treatment
- Use of androgens or other compounds for body building
- Use of retin-A or Accutane for the treatment of acne

Concomitant medications are discouraged except as prescribed for the treatment of intercurrent medical conditions. All concomitant treatments will be recorded on the subject's case record form (CRF), including the generic name of the drug, start and stop dates, and reason for use.

11. Study Materials

11.1 Study Medication

Each subject will receive the study medication assigned per the randomization list. The first dose will be administered at the clinic under the observation of the study staff. The day and time of the start of treatment will be recorded on the CRF in the appropriate space provided. The subjects will be given enough supply of medication (for 28 days) until their next visit.

Study medication log (diary) will be provided to the subjects for recording the time of application of gel. These medication logs will be reviewed at each visit. The investigator will retain the copies of these logs.

11.2 Storage

Study medications will be stored at a temperature not to exceed 25 C in a locked storage area at the study site. Study medication will be accessible only to study personnel designated to handle study medication.

11.3 Disposal

Empty used pill bottles will be returned to the clinic and retained at the site. All unused medication will be returned to the University of Washington investigational pharmacy for destruction once final drug accountability has been performed.

12. Study Procedures

12.1 General

There will be a total of three treatment groups as described in Section 7. The study will consist of 3 periods:

- 1. Pre-treatment period (including screening) for up to 60 days.
- 2. Treatment period for 24 weeks

3. Recovery period for about 12 weeks

The treatment period will begin with Day 1 of treatment, daily for 24 weeks. The recovery period will last for about 12 weeks.

12.2 Laboratory Samples

Blood samples for laboratory analyses will be collected at the two screening visits, Day 1 and at the treatment visits every four weeks with the subject in a fasting state (no food or drink other than 4 to 6 ounces of water or non-sweetened clear liquids for a minimum of 10 hours). If the subject is in a non-fasting state, the investigator will reschedule the visit within two days. The investigator will review all laboratory reports and file a copy with each subject's chart and CRFs. The CBC and blood chemistry samples will be analysed at the local hospital laboratory at the University of Washington.

The serum samples for measurements of retinoic acid will be frozen for analysis at the end of study to prevent inadvertent breaking of the blind. Briefly, the blood samples will be collected into vacutainers (containing serum separating tube gel and clot activator) and gently mixed. After wrapping in aluminum foil to prevent light exposure that can degrade retinoic acid, samples will be allowed to clot for 1-2 hours at room temperature before centrifugation at 1000-2000g for 15 minutes. Following centrifugation, the serum samples will be frozen at -20 C.

